Inclusion/exclusion criteria for peers: Inclusion criteria: (1) 50 years and older, (2) history of depression, (3) at least 5 years in recovery, and (4) received basic training in behavioral health or have volunteer experience in mental health. Exclusion criteria: (1) meet current diagnostic criteria for Major Depressive Disorder; (2) meet current diagnostic criteria for a manic episode or a psychotic disorder; (3) meet current diagnostic criteria for substance abuse disorder.

Inclusion/exclusion criteria for depressed older adults: Inclusion criteria are: (1) 50 years and older; (2) depressive symptoms with PHQ-9 scores ≥ 5 ; (3) belong to an underserved population, defined as annual income less than 200% of the federal poverty level (\$24,120) or self-identified ethnic minority; (5) able to communicate in English; and (6) willing to give informed consent. Exclusion criteria are: (1) meet diagnostic criteria for mania or hypomania; (2) meet diagnostic criteria for psychotic syndrome; (3) meet diagnostic criteria for substance abuse or dependence; (4) acutely suicidal; and, (6) a score on the Mini-Mental State Examination (MMSE) ≤ 24 .(41, 42) The Mini-Mental State Exam is a short standardized mental status examination that has been widely employed for clinical and research purposes for global assessment of cognitive functioning.(41) Clients who meet diagnostic criteria for severe depression, cognitive impairment, mania, hypomania, a psychotic disorder, or substance abuse or dependence will require clinical treatment. The research coordinator will also provide referrals for psychiatric care and list of community-based resources to the client. Eligible older adults will be scheduled for a clinical assessment.

Comparison condition. This group will receive 8 weekly visits and phone calls by study staff that will consist of social interaction. The staff member will receive training and receive supervision from the PI. The purpose is to provide social interaction that does not focus on peer support for depression, goal-setting nor self-care skills. Study

staff will monitor for worsening depressive symptoms and the client will be referred to mental health services as appropriate. The telephone visits will be audio-recorded and feedback given during weekly team meetings where study processes and problems will be discussed.

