Our primary study aim is to test the effects of the Peer Enhanced Depression Care Program for reducing depressive symptoms compared to Enhanced Usual Care. H1: Older adults randomized to the Peer Program (vs. control) will report decreased depression (PHQ-9 score decrease ≥ 5) at 8 weeks, 3, 6, 9 and 12 months. To assess the immediate effects of treatment, we will fit a mixed effects model(59) with nested random effects for counselor and participant such that $E[y_{ij}] = \beta_0 + \beta_1 tx + \beta_2 week + \beta_3 tx * week$, adjusted for sex and other covariates (see 7.a.), where y_{ij} is the PHQ9 score for the i th individual at intervention week j , β_2 is the rate of change in PHQ-9 for individuals randomized to EUC, and β_3 , the coefficient of interest, is the difference in rates of change in PHQ-9 between the Peer Program and Enhanced Usual Care study arms. To assess durability of the intervention effects, we will model PHQ-9 at each post-intervention follow-up (months 3,6,9 and 12) using a time-averaged model, which adjusts for PHQ-9 at week 8 and models PHQ-9 scores at later time points as a function of treatment assignment.

Sample size and power

We calculated power to detect a difference in rate of PHQ-9 decline over the 8-week intervention period via simulation. Assuming 20% attrition, design effect of 1.2 (to account for clustering within peers (62) based on ICCs from pilot data), and regression parameters from our preliminary data (SD of random intercept: 2.83; SD of random errors: 0.11), with N=160, we would have 99% power to detect a difference in slope of 0.625, which corresponds to a between-group difference of 5 points on the PHQ-9 at 8 weeks. Similarly, we calculated power to detect a sustained post-intervention between-group difference. We will have 99% power to detect a sustained 5-point difference in PHQ-9 during that period.

Data and safety monitoring plan

We will have a Data and Safety Monitoring Board (DSMB) to monitor the study with an attendant monitoring plan that will involve interim analysis. We will provide descriptive data for the first 6 months after the first participant has enrolled in the study to review both the non-serious and serious adverse event rates. We will meet every 6 months and also meet on an ad hoc basis if the real time serious adverse events warrant meeting, in their judgment.

d. Early stopping rules.

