At any time during the study, based on the findings of interim data analysis, the DSMB can put the study on either temporary hold or stop the study entirely after notifying the Principal Investigator and the IRB. In the unlikely case that results show that the intervention worsens depression, the study will be stopped.

7. Risks

- a. Medical risks, listing all procedures, their major and minor risks and expected frequency.

Older individuals, especially those with chronic illness, can easily feel overwhelmed or fatigued by what would be minimally demanding tasks for others, and, therefore, we include this discomfort in the potential risks. A minority of participants may respond to certain interview questions with feelings of sadness and grief (e.g., upon being reminded of interpersonal problems and social isolation). The Principal Investigator's experience as a researcher and psychiatrist has shown that when asking delicate questions and providing feedback on sensitive topics, the vast majority of participants have sufficient coping strategies to avert the extremes of behavior that put them at risk. Additionally, peer mentors are trained to be emotionally responsive with older adult participants to alleviate distress rather than increase distress. It is expected that older adults will feel relieved to meet with peer mentors who listen actively without being directive as has been our experience in the pilot study. We expect that the proposed study will provide older adult participants with benefits such as the discussion of psychological issues with the peer mentor that may offset the inconveniences or other consequences of participation.

Expression of suicidal ideation is always a risk when working with depressed participants. We will have a protocol in place to evaluate and manage patients who express suicidal ideation. We believe the risk that patients will experience due to this intervention is very low and are further minimized by the procedures we put in place, such as initial clinical evaluation prior to being matched with a peer and regular monitoring for depressive symptoms. The peer mentor will receive supervision by a clinical social worker and consultation by a geriatric psychiatrist as needed and available at all times by telephone or pager. In the case that suicidal ideation is identified, a clinical intervention (see below).

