Although we are not studying experimental drugs, the intervention is experimental with the attendant risks. To address this, we will have a Data and Safety Monitoring Board (DSMB) to monitor the study with an attendant monitoring plan. The role of the DSMB will be to ensure that no unexpected, untoward consequences of the experimental intervention occur, and if they do, to implement safeguards to decrease or eliminate future risks. Although the risk is low, the Peer Program could induce emotional distress associated with discussion of past trauma or current stressors. We will include as serious adverse events acts of suicide or attempted suicide and threats of violence or violence toward the research team, providers or outside personal contacts. Any adverse events related to behavior will be provided to the DSMB in real time. These adverse events include, but are not limited to, suicidality, homicidality, or inappropriate or threatening behavior with the research or clinical staff. Less serious adverse events related to the treatment of depression will be compiled and summarized for the DSMB at their scheduled meetings. All other severe adverse events in participants will be monitored by the Principal Investigator, the Study Coordinator, and the Social Workers and will be reported to the DSMB regardless of a priori expectation or investigator assessment of likelihood of the study being the cause of the adverse event.

The DSMB will also have the power to request further data (e.g. depression outcome data) from the Principal Investigator based on any concerns that may be raised in the ongoing investigation in the scientific community. Interim analyses will be performed and compiled for review by the DSMB. At any time during the study, based on its findings, the DSMB can put the study on either temporary hold or stop the study entirely after notifying the Principal Investigator and the IRB. In the rare case in which they have to do so, the DSMB will generate a formal report to the Principal Investigator, the sponsor (NIMH), and the IRB. This report would then be modified for a lay reader, a

version for past participants and current participants would be produced, and the letter would be sent to all past and current study participants and their referring providers.

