The DSMB will first meet 6 months after the first participant is enrolled to review both the non-serious and serious adverse event rates. They will meet annually and also meet on an ad hoc basis if the real time serious adverse events warrant meeting, in their judgment. The format of the meeting will include a presentation of the summarized data by the Principal Investigator and the Biostatistician. The absolute rates of adverse events as well as the rate compared between the intervention and control groups will be presented. After presentation by the study team, the DSMB will be left to confer alone. If deemed to be warranted, as described above, the DSMB can request a temporary hold be placed on the study until further data are reviewed.

- d. Legal risks such as the risks that would be associated with breach of confidentiality.

For older adult participants, risks regarding breach of confidentiality and disclosure of clinical information exist and may be heightened due to use of non-professional peer mentors in the proposed study. Should confidentiality safeguards fail, there is potential harm in the form of social risks and disclosure of private information. However, the risks of participation should be no more than minimal, with effective confidentiality safeguards. The safeguards include the following: 1) Peer mentors will sign a contract of confidentiality agreement before participating in the project, receive confidentiality training and the importance of confidentiality will be stressed throughout training and supervision sessions on a weekly basis. 2) Older adult participants will be informed that absolute confidentiality cannot be guaranteed but study staff will put rigorous procedures in place. In our experience, there were no known breaches of confidentiality in our pilot study, older adults did not express concern about this during the consent process, and none dropped out of the study for this reason. All information collected will be coded with a study identification number and will be stored in locked files that only staff associated with the study can access. These records will be protected by the confidentiality system of Massachusetts General Hospital and will not be disclosed except as required by law. Audio recordings will be saved in Massachusetts General Hospital OneDrive.

- e. Financial risks to the participants.

There are no costs to the participant associated with the study and we do not foresee financial risks to them.

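### Section 7.c limits the less serious adverse events compiled for the DSMB to those tied to depression treatment, which conflicts with the unrestricted non-serious event rates promised in Sections 6.c and 7.c

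*Combined protocol and SAP*

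**What the plan says.** Section 7.c gives three routes by which adverse events reach the DSMB.

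- Behaviour-related events: "Any adverse events related to behavior will be provided to the DSMB in real time". The examples are suicidality, homicidality and inappropriate or threatening conduct, and the list is open-ended. No condition on severity or relatedness is attached.
- Less serious events: "Less serious adverse events related to the treatment of depression will be compiled and summarized for the DSMB at their scheduled meetings".
- Other severe events: these are "reported to the DSMB regardless of a priori expectation or investigator assessment of likelihood of the study being the cause of the adverse event".

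Two places describe what the DSMB will look at. Section 6.c (Data and safety monitoring plan) has descriptive data supplied "to review both the non-serious and serious adverse event rates". A later paragraph of Section 7.c says: "The DSMB will first meet 6 months after the first participant is enrolled to review both the non-serious and serious adverse event rates". It then adds: "The absolute rates of adverse events as well as the rate compared between the intervention and control groups will be presented". Neither place mentions relatedness.

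Two other sections bear on how the qualifier would work. On the comparison condition, Section 4.a says: "The purpose is to provide social interaction that does not focus on peer support for depression, goal-setting nor self-care skills". Section 7.a, on risks, says: "A minority of participants may respond to certain interview questions with feelings of sadness and grief". It also counts fatigue or feeling overwhelmed by undemanding tasks among the potential discomforts.

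**The concern.** The sentence on less serious events is the only one in the documents that says which of them are compiled, and it carries a relatedness qualifier. The sentence on severe events sets attribution aside, and no reason is given for treating the two classes differently.

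Two consequences follow if the sentence is applied as written. First, a reaction provoked by an assessment interview rather than by depression treatment falls outside the wording, in both arms. Second, the wording refers to something that one arm delivers and the other is designed not to focus on, so the same kind of event could be compiled in one arm and left out in the other.

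What is at stake is the between-arm comparison of non-serious event rates shown to the DSMB, which can ask for a temporary hold. If the numerator depends on attribution to treatment, a difference between arms may reflect the counting rule rather than the participants' experience. Equally, a reassuring table may omit procedure-related distress. No efficacy analysis is affected.

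**Working it through.** The plan states no adverse event rate and no share of events judged related, so there is no figure to reproduce. The check sets the relevant sections side by side. I take less serious (7.c) and non-serious (6.c and 7.c) to mean the same class of event; the documents do not say otherwise.

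1. *Compilation rule against review content.* The compilation sentence in 7.c restricts less serious events by relatedness. Section 6.c and the later paragraph of 7.c promise non-serious rates without restriction. If the compilation sentence governs, the rates reviewed are rates of treatment-related events only, and the review text does not say so. If the review text governs, the qualifier has no function. Staff preparing the DSMB tables cannot tell which applies.

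2. *Less serious against severe.* For other severe events, expectation and judged cause are explicitly irrelevant. For less serious events, relatedness is a condition of being compiled. The two rules are in adjacent sentences.

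3. *Assessment-related distress.* Section 7.a names sadness or grief at interview questions, and fatigue or feeling overwhelmed. Section 4.b gives both arms the same number of study visits, so these reactions can arise in either arm. Taking the three routes in turn: they are not obviously behaviour-related, judging by the listed examples; they do not come from depression treatment; and if less serious, they are not severe. No route clearly applies.

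4. *Fit of the qualifier by arm.* Section 4.a describes the peer mentors as delivering depression care, and the control as social interaction not focused on depression support. An event arising from a peer session meets the wording easily; one arising from a control call does so less readily. Control events can still qualify through other care: Section 4.a provides for referral of control participants to mental health services, and Section 4.d leaves participants free to obtain depression care outside the study.

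5. *Who applies the qualifier.* Section 4.c blinds only the person conducting the post-study assessment. No section says who judges the relatedness of less serious events, or whether that person knows the allocation.

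6. *Why no size is given.* Suppose each arm has n participants and the same true event rate r, and that shares p1 (peer) and p0 (control) are judged related. The DSMB would then see a rate ratio of (n × r × p1) / (n × r × p0) = p1 / p0. Sample size and event rate cancel, so the apparent ratio is simply the quotient of two shares that the documents do not supply. Any number put on it would restate the assumption.

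**The case against.** The strongest reply is that the DSMB is not confined to treatment-related events. Sections 6.c and 7.c promise non-serious rates without a filter, and the real-time route for behaviour-related events has no filter and an open-ended list. This stands against a reading on which less serious events reach the DSMB only when treatment-related. It does not remove the problem: it turns it into a contradiction between the compilation sentence and the review text.

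A reader might also infer that control events can hardly ever qualify, that the comparison is therefore biased towards more events in the peer arm, and that staff who know the allocation make the judgement. The documents support none of these as fact. The phrase is undefined and could cover any depression care. Control participants may be referred or use outside care; if they used more of it, the direction could reverse. The person judging relatedness is not identified.

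Finally, Section 7.a names risks. It does not say that a passing reaction during an interview would be recorded as an adverse event. Loss of such events from the summaries is thus a consequence of reading the compilation sentence literally, not a stated exclusion. It is also fair to say that depression itself is tracked separately with scheduled PHQ-9 measurements, and that the stated stopping ground in Section 6.d is worsening of depression, not a ratio of less serious events. This limits the consequences. It does not justify leaving the safety tabulation undefined.

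**Conclusion.** The point holds as an internal inconsistency with a plausible effect on a safety comparison. The sentence in 7.c that restricts less serious events conflicts with the unrestricted non-serious rates in 6.c and in the later paragraph of 7.c. It also departs from the rule for severe events in the next sentence. Taken literally, it leaves assessment-related distress or fatigue without a clear compilation route and allows capture to differ by arm.

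Neither the size nor the direction of any distortion can be established from the documents. The conclusion rests on a literal reading of the compilation sentence and on treating less serious and non-serious as one class. It does not depend on any assumed event rate, or on who judges relatedness. The change is worth making because it is small and bears on the between-arm comparison the DSMB will see.

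**What to change.** Reconcile Section 6.c with both paragraphs of Section 7.c, using one definition of the events compiled for the DSMB and applying it identically to both arms. The direct way is to delete from the compilation sentence in 7.c the words that tie less serious events to depression treatment. All recorded less serious adverse events would then be compiled and summarised by arm regardless of attribution, as 7.c already does for other severe events. If relatedness is collected, show it as a descriptive column and not as a condition for inclusion.

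This governs which recorded events are tabulated. It leaves referral, safety management and the real-time reporting route unchanged.

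The cost is one sentence of protocol wording and slightly longer DSMB listings, with no added visits or staff.

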Training for peer mentors. We developed a training program that was used in our pilot study. Study staff will conduct 5 sessions totaling 20 hours of training using videoconference that will serve as an introduction to the peer mentor role with continued training and skills development occurring during the supervision meetings. Training will include taking a client-centered approach, using effective communication skills, including appropriate self-disclosure, client and peer safety and client confidentiality, expression of empathy, active listening, goal-setting, sharing coping skills and other depression self-care skills. Establishing relationship boundaries is critical to ensuring that clients benefit from peer support. Training on this issue will be provided initially and continually reinforced in supervision meetings. Training will also include experiential learning, role-play, and discussion of client cases. The peers will receive training in appropriate use of audio-recordings during the meetings with participants, the submission of the audio-recordings to the clinical supervisor on a weekly basis and the handling of the recordings overall. After completion of training, study staff will assess peer mentors for suitability to be matched, taking into consideration attendance, active participation, commitment and demonstration of interpersonal and communication skills. Those peers who exhibit core peer skills and commitment will be matched with clients. Peer mentors will be paid for meetings with the depressed older adults and supervision meetings with the social worker.

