8. Benefits

- a. Description of the probable benefits for the participant and for society.

The proposed study may benefit the older adult participants in terms of psychoeducation and self-care skills associated with depression, monitoring of symptoms and services delivered by a peer mentor who is under a mental health professional's supervision. The peer may benefit from increased sense of self-efficacy in helping another person and will have an increased knowledge base from the mental health training provided by the study. Benefits to society may include new knowledge regarding the provision of mental health services in the community. If the peer program is successful, new ways to provide depression care services in the community setting to low-income minority older adults will be established. The risks to the patient for participating in this project are minimal and the possibility of improving depression care is substantial.

A.4. Importance of knowledge to be gained

This research will inform the development of peer programs whose aim is to improve access and engagement of depression care among minority and low-income populations. Given that minority older adults receive inadequate or no mental health care and are less likely to access traditional mental health services, developing new methods of delivering depression care is important.

9. Payment and Remuneration

- a. Detail compensation for participants including possible total compensation, proposed bonus, and any proposed reductions or penalties for not completing the protocol.

Peer mentors - Each peer will participate in 20 hours of training conducted by the PI and also meet weekly for supervision with the social worker for each contact hour with the client. Peer mentors will be paid \$100 for attending 20 hours of training. They will be only be paid if training is completed and they are successfully matched with a

least 1 depressed older adult participant. Peer mentors will be also paid a total of \$50 for 1 meeting with a client and 1 supervision meeting. For each older adult who will receive 8 meetings with the peer, peer mentors will receive \$400. They will receive an additional \$20 for a post-study interview.

Older adult incentives - Participants will be given a token of appreciation of \$30 with for one (1) baseline assessment meeting, 8 week assessment, 3, 6, 9 and 12 month follow up assessments for total of 6 assessments for a total \$180.

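### The Principal Investigator helps present between-arm adverse event rates to the DSMB while supervising the control staff, and nothing restricts access to compiled comparative results

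*Combined protocol and SAP*

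**What the plan says.** **DSMB meetings (Section 7.c).** "The format of the meeting will include a presentation of the summarized data by the Principal Investigator and the Biostatistician". On content: "The absolute rates of adverse events as well as the rate compared between the intervention and control groups will be presented". On privacy: "After presentation by the study team, the DSMB will be left to confer alone". So private deliberation is provided for, but a closed presentation is not.

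**Interim results (Sections 6.d and 7.c).** Section 7.c says "Interim analyses will be performed and compiled for review by the DSMB", without saying who prepares them, what they contain or who else may see them. It also lets the DSMB ask the Principal Investigator for further data and gives depression outcomes as the example. Section 6.d stops the study if results show that the intervention makes depression worse.

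**The investigator's part in delivery.** For the control arm, Section 4.a (Comparison condition) says: "The staff member will receive training and receive supervision from the PI". Control calls are recorded, and feedback on them is given at weekly team meetings. For the peer arm, Section 9.a says "Each peer will participate in 20 hours of training conducted by the PI", whereas Section 4.a (Training for peer mentors) says "Study staff will conduct 5 sessions totaling 20 hours of training using videoconference". Section 4.a assigns weekly supervision of peers to licensed clinical social workers.

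**Blinding (Section 4.c).** Only the post-study assessor is blinded.

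The documents contain no rule limiting who on the study team may see comparative results.

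**The concern.** There are two kinds of knowledge here. One is which participant is in which arm, which the investigator and staff must have in a trial of this kind. The other is how the arms compare in aggregate. Nothing in the intervention requires the investigator to have that second kind during the trial, yet the stated meeting format supplies it for adverse events.

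It matters because of the investigator's continuing role. The control condition is defined largely by what staff must leave out: peer support for depression, goal-setting and self-care skills. Keeping to that depends on supervision, and the supervisor is one of the people presenting the comparison. Someone who has seen compiled results could, without meaning to, supervise control calls differently, pursue follow-up more actively in one arm, or refer more readily. An analysis of the final data could not reliably remove such an effect.

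The adverse events are also not remote from the primary outcome. Section 7.c counts suicidality among them, and Section 7.b notes that the PHQ-9 has an item on suicidal ideation.

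**Working it through.** The plan gives no figure on this point to reproduce, and no power or alpha calculation applies. The check has two parts: what the investigator is shown, and whether the meetings fall during delivery.

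**1. What the investigator is shown**

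| Item | Source | Status |
|---|---|---|
| Adverse event rates compared by arm | 7.c | Stated |
| Depression outcome data requested by the DSMB | 7.c, request goes to the Principal Investigator | By-arm access inferred |
| Interim analyses | 7.c, prepared for the DSMB | Content and access not stated |
| Evidence on worsening of depression | 6.d | Applying the rule needs interim depression results; who sees them is not stated |

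**2. Which arm the investigator can affect**

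- Control arm: supervision is direct and continues throughout delivery (4.a).
- Peer arm: the link is weaker. Sections 4.a and 9.a disagree on who delivers the training, and social workers supervise peers during delivery. Training is completed before a peer is matched. The first DSMB meeting is 6 months after first enrolment, so peers matched before then were trained before any presentation.

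**3. Meetings during delivery**

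Inputs: 160 participants (Section 2); 5 to 7 enrolled per month (4.a); 8 weekly sessions (4.a); first DSMB meeting at month 6, then annually (7.c) or every 6 months (6.c).

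Formulas, with 4.345 weeks to the month:
- enrolment months = 160 / rate
- end of delivery = enrolment months + 8 / 4.345 = enrolment months + 1.8

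| Rate per month | Enrolment (months) | End of delivery (month) | Six-monthly meetings by then | Annual meetings by then |
|---|---|---|---|---|
| 5 | 160/5 = 32.0 | 33.8 | 6, 12, 18, 24, 30: five | 6, 18, 30: three |
| 6 | 160/6 = 26.7 | 28.5 | 6, 12, 18, 24: four | 6, 18: two |
| 7 | 160/7 = 22.9 | 24.7 | 6, 12, 18, 24: four | 6, 18: two |

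That is 2 to 3 meetings if annual, 4 to 5 if six-monthly, and 2 to 5 overall.

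At the month-6 meeting, 5 × 6 = 30 to 7 × 6 = 42 participants would be enrolled, leaving 160 − 42 = 118 to 160 − 30 = 130 still to enter. Most of both arms would therefore be delivered after the first comparative presentation.

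**Caveat.** Section 4.b gives a duration of 18 months. If that means the whole trial, 12-month follow-up leaves at most 6 months for enrolment, or 30 to 42 participants at the stated rate. The counts above therefore rest on the enrolment target and not on the 18 months.

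**The case against.** The strongest reply is that the harm rests mostly on inference and that a firewall would achieve little.

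- **Only adverse events are stated.** A reader might infer that the investigator learns at every meeting which arm is ahead on depression. The documents do not say so. By-arm presentation is specified for adverse event rates only, and depression data are something the DSMB may request. The stopping sentence makes interim depression results necessary but does not place them before the investigator. This part of the objection stands.
- **Events are already visible.** Section 7.c has the investigator help monitor severe adverse events, and in an open trial of 160 these could be counted by arm. This also stands. The main gain from a closed session is for compiled rates and any interim PHQ-9 comparison.
- **The peer-arm link is thin.** A reader might infer that the investigator directs delivery in both arms. Continuing supervision is documented for the control staff only.
- **Other safeguards exist.** The intervention is manualized, fidelity is checked with checklists, and sessions in both arms are recorded. These constrain delivery and could reveal drift, but they do not remove an avoidable exposure, and they do not govern retention effort.
- **A monitoring plan may exist.** Sections 6.c and 7.c mention one. It might set access rules, but Section 7.c itself states the meeting format, and that format has the investigator presenting.
- **The statistician is not detached.** Section 4.a says the study statistician wrote the allocation software. That is a limitation of using the existing Biostatistician, but it is no reason to keep the investigator in the comparative presentation.

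**Conclusion.** The point holds. Section 7.c positively places between-arm adverse event rates before the person who supervises the control staff, and nothing restricts that person's access to other comparative results. Exposure to between-arm PHQ-9 results is possible but inferred. The plausible routes of influence are control delivery, retention effort and referral; the route into peer delivery is weak.

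The exposure is about 2 to 5 scheduled meetings during delivery, assuming enrolment of 5 to 7 a month and excluding ad hoc meetings. A reader might count meetings to the end of 12-month follow-up instead. With the last follow-up at month 22.9 + 12 = 34.9 to 32.0 + 12 = 44.0, that gives 3 to 7. Meetings after delivery ends cannot affect delivery, however, and bear at most on retention and referral.

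The size of any bias cannot be computed from the documents, and nothing here shows that bias will occur. The change is worth making because the exposure is avoidable, its effect could not reliably be undone in analysis, and the remedy is cheap.

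**What to change.** Revise the DSMB text in Section 7.c, and align Sections 6.c and 6.d with it:

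1. **Open session.** The Principal Investigator presents accrual, retention and adverse events pooled across arms.
2. **Closed session.** The existing Biostatistician alone presents arm-level event rates and any interim PHQ-9 results to the DSMB.
3. **Data requests.** DSMB requests for depression outcome data go to the Biostatistician.
4. **Access rule.** The Principal Investigator does not see compiled arm-level results until database lock, unless the DSMB releases them for safety.
5. **Unchanged.** Monitoring and reporting of individual adverse events continue as planned.
6. **Reconcile.** Sections 6.c and 7.c must agree on meeting frequency, and Sections 4.a and 9.a on who trains the peers.

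The cost is wording in the DSMB plan, with no new staff and no change to sample size or alpha. There are two downsides: the investigator cannot comment on arm-level tables in the meeting, and the firewall is only partial for adverse events, which the investigator sees one by one in an open trial.
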